optional participant satisfaction survey at end of study (via smartphone), step count and floors climbed (via the Fitbit device), medical and pharmacy claims data (including up to 36 months history for eligibility confirmation), HRU and health economics (including hospitalization/readmission due to HF or other reason, ED visits, the duration of stay at each hospitalization/readmission), review of claims for prohibited medications and new diagnoses that may require discontinuation, and adverse events. In addition, information related to outpatient IV diuretics, inotropes and vasodilators and in-patient IV therapies as well will be considered relevant. Note that claims data that involves up to 36 months history to confirm eligibility into this study will not be part of the study database for analysis.

Participants will be of any gender, 18 years of age or older, and will have clinically stable, symptomatic HF with or without type 2 diabetes mellitus (T2DM) with a KCCQ overall summary score <80 prior to randomization, which represents New York Heart Association (NYHA) II and III participants.

Figure 1: Schematic Overview of the Study

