1.6. Study Data Flow

Data flow in this study is facilitated by an automated integrated process that extracts clinical data from 3 sources: PRA mobile health platform [PRA mHP], Care Innovations, and Symphony. These data are loaded into PRA's Common Clinical Data Store (CCDS) where the data is accessible by JReview for data validation and analysis, as well as for extraction into RAW and SDTM datasets. This automated Extract-Transform-Load (ETL) process will utilize a data container on Amazon Web Services (AWS), referred to as the "Data Analytics Container" or "DAC", which is managed by PRA. A more detailed data flow diagram is provided in Appendix 5 of this SAP.

The PRA mHP platform serves as the main hub for source data capture on the CHIEF-HF study. It captures eConsent, information entered by Health Network Systems (HNS) from a participant's electronic medical records (EMRs), participant status overseen by Care Innovations (CI), randomization through integration with Endpoint IRT, drug shipment through integration with Marken, primary and secondary endpoint data from ePROs (KCCQ, PGI-S, PGIC), dosing compliance, as well as activity measured by the Fitbit watch. PRA mHP data will go into the DAC via a direct database connection. Medical and pharmacy claims data is contained within Symphony

Health Solutions and exists as completely de-identified data. This includes data used in the study to review and analyze adverse events, healthcare resource utilization (HRU) and health economics (including hospitalization/readmission due to Heart Failure [HF] or other reason, Emergency Department (ED) visits, the duration of stay at each hospitalization/readmission), as well as review of prohibited medications and new diagnoses that may require discontinuation.

Symphony claims data will be pulled into the DAC for participants randomized into the study via PRA mHP eConsent and will be mapped to SDTM as detailed in the SDTM specifications relevant to the study protocol and SAP. The collection timeframe for claims associated with AEs of special interest will begin on the Informed Consent Date through the End of Treatment + 30 days. The collection timeframe for Pharmacy claims of prohibited concomitant medications (SGLT2i) will begin on the ICF date through End of Treatment. The collection timeframe for claims associated with Health Resource Utilization will begin on the ICF Date through the 9-month observation period.

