Baseline for daily step count and daily floors climbed variables will be defined by averaging the daily values over a 14-day interval starting with the first dose date. These data will be organized into a vertical file format to read one record per participant for averages over each 2-week interval during the entire study (including the EOT/EOS values, as applicable).

Claims Data – AEs, HRUs, Clinical Outcomes

Claims data pertaining to AEs of interest (as defined in the protocol), number of prescription fills, HRUs, and clinical outcomes reported with appropriate ICD codes applied at the individual participant level will be organized with one record for each incident (ie, hospitalization, etc.) date. Adverse events of interest include all severe hypoglycemic events, acute kidney injury, fractures, diabetic ketoacidosis, and lower limb amputation.

In addition, the following adverse events will be examined: hypotension; Fournier’s gangrene; genital mycotic infections; urinary tract infections (including urosepsis and pyelonephritis); increased urination; and hypersensitivity reactions including angioedema and anaphylaxis.

Self-reported AE data – Data from participants self-reporting adverse events (AEs) to a Call Center (set up by Care Innovations) will be manually submitted directly to the Sponsor (i.e. Janssen Safety [GMS]) for appropriate evaluation and analysis. Janssen Safety (GMS) will extract participant-reported AEs and transfer data to PRA for upload into the CCDS. Self-reported events will be captured from the date of the first dose of study intervention through the end of treatment (Month 3) plus 30 days. A listing of these self-reported AE may be produced based on available data.

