6.1. Adverse Events

All AE data summaries will be based on the safety analysis set except where stated otherwise. A treatment emergent AE is defined as an event that occurs after the first dose of study intervention (Study Day 1) and/or worsens in severity during the double-blind treatment period.

Adverse events self-reported to the Call Center will be assessed by Janssen Global Medical Safety (GMS) for start and end dates, causality and meeting SUSAR reporting requirements. If the specific dates pertaining to the self-reported AEs are unknown, there will be limited follow-up for resolution. For any events still ongoing at the end of the study, there will be no follow up (as the Call Center will be closed at that point) possible. Adverse events will be coded according to MedDRA and will be reported by preferred term for each randomized intervention group. Janssen Data Management will request a listing of all AEs/SAEs reported to the Call Center from the Janssen GMS. This listing will be shared with PRA (external vendor) to convert the information

into the SDTM format and for inclusion in the final SDTM data package for summary by various subgroups (e.g., T2DM and non-T2DM).

Adverse events collected through the claims database will be analyzed separately for the 12-week treatment period + 30 days after last dose and the 9-month entire study period respectively. It is assumed that claims database will have dates of service provided (procedure dates, office visits, hospital admissions, etc.) but not actual start/end dates of events prior to claims being filed. Therefore, no imputation of AE start/end dates will be feasible based on the claims data. Dates of service(s) rendered to participants during the study (i.e., starting from the time informed consent is signed until the end of double-blind treatment plus 30 days) will be taken into account. The claims data will utilize ICD codes to identify the SAEs and AEs of interest which are defined in the protocol and for the final analysis. The AEs of interest include all severe hypoglycemic events, acute kidney injury, fractures, diabetic ketoacidosis, and lower limb amputation. In addition, hypotension, Fournier's gangrene, genital mycotic infections, urinary tract infections (including urosepsis and pyelonephritis), increased urination and hypersensitivity reactions (including angioedema and anaphylaxis) will be considered for coding and final analysis.

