For the prohibited medications, analysis period will include data from the date of informed consent until the end of double-blind treatment period. For all other concomitant medications, analysis period will include data from the date of informed consent until the end of the study. For the HRU data analysis, information collected from date of informed consent until the end of study will be considered in the final analysis.

For both the double-blind treatment period + 30 days after last dose and the 9-month entire study period, descriptive summaries (numbers and percentages) of participants having an SAE/AE of interest will be produced, including by participant's diabetes status (T2DM and non-T2DM) and by randomized intervention group. Discontinuations (and reported reasons) will be summarized by randomized intervention group based on available claims data.

There will be no reconciliation/analysis of SAE/AE data that are self-reported to the Call Center with the data obtained from the claims database.

A listing will be presented for treatment emergent hospitalizations and deaths for each randomized intervention group. AEs occurring between informed consent and the day prior to the first dose of study intervention will also be listed. This listing will be based on participants with informed consent into the study. Depending on the claims/pharmacy data, AEs occurring in participants who used prohibited (commercially available SGLT2is other than the study intervention, canagliflozin) will also be listed.

Based on pharmacy profiles of the participants after-consent in this study, the total number of participants concomitantly receiving UGT inducers during the double-blind treatment period will be summarized combined across both study intervention groups. If the number of such participants is >2% of the total 1,900 targeted for enrollment in this study, the users and non-users of UGT inducers will be summarized by each study intervention group as well and examined further (as

necessary) for any relationship to key study outcomes (eg, PRO endpoints and clinical outcomes reported in claims).

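### The adverse-event-of-interest list omits volume depletion and four of five lower-limb stopping conditions, so non-serious office-coded cases have no planned by-arm count from claims

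*SAP*

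**What the plan says.** Protocol 8.3.4 sets the list, and SAP 5.1.2 repeats it: "Adverse events of interest include all severe hypoglycemic events, acute kidney injury, fractures, diabetic ketoacidosis, and lower limb amputation". Both add six further events to be examined: hypotension, Fournier's gangrene, genital mycotic infection, urinary tract infection, increased urination and hypersensitivity. SAP 6.1 carries all of these into coding and the final analysis.

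SAP 6.1 opens its claims text in general terms: "Adverse events collected through the claims database will be analyzed separately for the 12-week treatment period + 30 days after last dose", and likewise for the 9-month period. The working sentences are narrower. Identification is restricted ("The claims data will utilize ICD codes to identify the SAEs and AEs of interest which are defined in the protocol"), and so is the table: "descriptive summaries (numbers and percentages) of participants having an SAE/AE of interest will be produced", by diabetes status and by randomized group.

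Two other by-arm outputs are relevant. Self-reported events "will be reported by preferred term for each randomized intervention group". For stopping of study drug: "Discontinuations (and reported reasons) will be summarized by randomized intervention group based on available claims data".

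Protocol 7.1 requires study drug to be stopped for any of five lower-limb conditions: new active skin ulcer, osteomyelitis, gangrene, critical ischemia or amputation. Protocol 4.3 counts volume-related events among the dose-dependent harms and says they are fewer at 100 mg.

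**The concern.** The protocol requires no clinic visits, and the SAP marks laboratory tests, vital signs and physical examination as not applicable. A by-arm safety comparison therefore rests on claims and self-reports. In that setting, an event with no code group in the claims table is compared between arms only if it is serious, self-reported or recorded as the reason for stopping drug.

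The protocol itself marks the omitted events as important. When its Introduction argues that canagliflozin is safe in heart failure, it names volume depletion together with fracture, amputation, osmotic diuresis and acute kidney injury. Oral diuretics are expected background treatment, and entry with preserved ejection fraction requires a loop diuretic or a mineralocorticoid antagonist. The four missing limb conditions are entry exclusions (protocol 5.2) and mandatory stopping reasons (7.1), and protocol 4.1 has claims monitored for diagnoses that require discontinuation.

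What is at stake is the completeness of the descriptive safety report. Efficacy results, error rates and power are not involved.

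**Working it through.** The plan gives no figure to reproduce. The check is a comparison of lists and of scope.

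**1. Count the list.** Protocol 8.3.4 and SAP 6.1 each give 5 events of interest plus 6 further events: 5 + 6 = 11. All 11 match between the two documents.

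**2. Compare the list with the events the protocol singles out.**

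| Event | Where the protocol raises it | On the list? |
|---|---|---|
| Volume depletion/dehydration | Introduction; 4.3 (volume-related events) | No; nearest terms are hypotension, acute kidney injury and increased urination |
| New skin ulcer | 5.2, 7.1 | No |
| Osteomyelitis | 5.2, 7.1 | No |
| Lower-extremity gangrene | 5.2, 7.1 | No (Fournier's gangrene is not a limb condition) |
| Critical ischemia | 5.2, 7.1 | No |
| Amputation | Introduction; 5.2, 7.1 | Yes |

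Of the five limb stopping conditions, 1 is listed and 5 − 1 = 4 are not. Of the five harms named together in the Introduction, fracture, amputation and acute kidney injury are listed, and increased urination is close to osmotic diuresis. Only volume depletion has no counterpart.

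**3. Compare scope.** Protocol 8.3.1 and the matching synopsis text aggregate claims adverse events for treatment + 30 days by assignment, with no list. The synopsis also has claims events categorized by diagnosis code. Protocol 8.3 and 9.4.3 restrict the claims aggregation to non-endpoint SAEs and adverse events of interest. SAP 6.1 takes the narrower scope. It matches 8.3, 8.3.4 and 9.4.3, and it is narrower only than 8.3.1 and the synopsis.

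**4. Follow an office-coded, non-serious case through the other outputs.**
- *SAEs:* admissions are covered, and protocol 8.3 and 9.4.3 include emergency department visits. Office-only cases are not.
- *Self-reports:* SAP 6.1 plans preferred terms by arm. However, SAP 5.1.2 says only that a listing may be produced, SAP 2.1 summarizes self-reports only to Day 87, and SAP 6.1 plans no reconciliation with claims. The route also depends on the participant calling.
- *Discontinuation reasons:* a limb case can appear here if it is recorded as the reason. A case first coded after the last dose cannot. Volume depletion is not a named stopping condition, so it appears only if drug was stopped under the general safety or tolerability criterion.

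Each route catches some cases. None gives an incidence by arm from claims.

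**5. Precision of the added rows.** SAP 1.4 anticipates 400 to 480 participants, so 400/2 = 200 to 480/2 = 240 per arm. One participant is then 1/240 = 0.4% to 1/200 = 0.5% of an arm.

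**The case against.** The strongest objection is that the SAP does what the protocol tells it to do. A reader who sets SAP 6.1 beside protocol 8.3.1 might infer that the SAP departs from the protocol. The documents do not support that. Section 8.3.1 concerns the timing of collection, while 9.4.3 is the protocol's analysis section, and the SAP agrees with 9.4.3, with 8.3 and with the list in 8.3.4. This part of the objection stands in full. The omission originates in 8.3.4, and the mismatch with 8.3.1 is internal to the protocol.

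It can also be said that stopping rules and reporting lists serve different purposes and need not match. Starting another SGLT2 inhibitor and pregnancy are stopping criteria too, and neither is an event of interest. Amendment 2 expanded the list, the sponsor describes the safety profile as well established, and 4.3 mentions volume events to explain why the lower dose was chosen. That is fair, and no document requires the two lists to agree. But the omitted limb conditions are clinical harms, and amputation from the same stopping criterion was thought worth listing.

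Finally, existing coverage is broad: hypotension, acute kidney injury, increased urination, SAEs, a by-arm listing of treatment-emergent hospitalizations and deaths, self-reports, and discontinuation reasons. This narrows the point to non-serious cases seen only in office claims. It does not remove it.

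**Conclusion.** The point holds as a cheap improvement. Volume depletion/dehydration and four of the five limb stopping conditions are missing from the list in protocol 8.3.4, and hence from SAP 5.1.2 and 6.1. Non-serious, office-coded cases of these events have no planned by-arm incidence from claims. This assumes that the specific sentences in SAP 6.1 govern the table, rather than its general opening statement about claims.

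Two stronger readings should be avoided. A reader might infer that these events would go unreported altogether; the partial routes above show otherwise. A reader might also try to size the loss by the share of follow-up that falls after the last dose. Calendar time says nothing about how many cases occur or are missed, and the documents give no rates for the omitted conditions. The number missed is unknown, and none is assumed here.

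**What to change.** Add two ICD-10 groups to protocol 8.3.4 and to SAP 5.1.2 and 6.1:

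- volume depletion/dehydration, with a combined volume-related row that also counts hypotension;
- lower-limb skin ulcer, osteomyelitis, gangrene or critical ischemia, with a combined lower-limb row that also counts amputation.

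Report both descriptively, by arm and T2DM status, in the treatment + 30 days table already planned. That window fits the claims extraction in SAP 1.6 for events of special interest, which "will begin on the Informed Consent Date through the End of Treatment + 30 days". Fix the code lists before unblinding.

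Define a new event as one whose first code falls on or after Study Day 1, with no such code between consent and Day 1. A longer look-back is not available, because the 36-month claims history "will not be part of the study database for analysis". Under the protocol schedule the look-back is at most about 28 + 7 = 35 days. The SAP should state that some carried-over codes may be counted as new in both arms; the 6-month entry exclusion for active limb conditions limits this for the limb group. Separately, align the wording of protocol 8.3.1 with 9.4.3.

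The cost is two code lists and a slightly longer table, from claims already linked. Limb diagnoses are already monitored there; volume depletion needs a new code set. The drawback is imprecise rows at 200 to 240 participants per arm.

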- For daily activity measured by daily step counts, total active days (defined as Fitbit recorded ≥ 100 steps) and percent of active days to total days spent in the study analysis period will be summarized for each intervention group using mean and SD. Level of daily activity will also be described using categories of total step counts per day – 1) < 3000 steps per day (low activity/sedentary), 2) 3000-5999 (moderate activity), and 3) ≥ 6000 steps per day (high activity). Associations between daily step count (categorized into activity levels) and baseline characteristics (eg, age, sex, race, T2DM status, EF type, etc.) will be examined using a 1-way ANOVA for continuous data values and the Fisher exact test for categorical data.
- Correlation between total step counts per day and clinical events (eg, # of outpatient intravenous therapies, # ED visits, # hospitalizations, etc.) will be described for the double-

blind treatment period and total study duration separately. Relationships between change in step counts/floors climbed and incidence of reported clinical outcomes and PRO measures will be examined at the end of the double-blind treatment period and end of study separately.

- Daily floors climbed will be summarized by each intervention group for the double-blind treatment period and over the entire study duration separately.
- Descriptive statistics (ie, N, mean, SD, minimum and maximum) will be presented for total HRU and health economics data for each intervention group separately for the double-blind treatment period and the observational (no intervention) period. HRUs and health economics data typically include information regarding participants using health services for managing any clinical events/illnesses, hospitalizations/ED visits, surgeries, medication issues/prescription changes, and costs incurred.
- Descriptive statistics will be presented for participant's satisfaction with his/her experience with the virtual design at the end of the study.
- Using data from claims, the number of outpatient intravenous therapies, ED visits, and hospitalizations by each intervention group will be summarized. These summaries will include descriptive statistics.

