- Using data from the claims and data on deaths, time to first hospitalization/readmission for heart failure, time to first hospitalization/readmission for other events, and time to death will each be analyzed using a Cox's regression model both for the double-blind treatment period and the entire study duration and include terms for study intervention and stratification factor (HFrEF/HFpEF). Hazard ratios, corresponding 95% CIs, and associated p-values will be presented. Distribution of the times to first hospitalization/readmission for HF, time to first hospitalization/readmission for other events, and time to death will be displayed with Kaplan-Meier curves. Participants who do not experience any such events of interest during the study analysis period will be considered 'censored' in these analyses.

No adjustment for multiplicity will be performed for the exploratory analyses listed above.

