9. HEALTH ECONOMICS

As treatment of participants with symptomatic HF with JNJ-28431754 (canagliflozin) versus placebo may result in lower utilization of hospitalization/readmissions due to HF or other reason, ED visits, the duration of stay at each hospitalization/readmission, and discharge destination will be summarized by each intervention group. Comparison will be made between groups by analyzing differences in hospitalizations/readmissions and ED visits using the Fisher exact test. Descriptive statistics (eg, mean, median, minimum, and maximum) will be provided for the total length of stay in hospitals for each intervention group. Cumulative distribution function of the time to first occurrence of hospitalization/readmission will be estimated by the Kaplan-Meier method and tested using a log-rank test, stratified by the type of HF ejection fraction (ie, HFrEF or HFpEF). In addition, a Cox proportional hazards model with intervention and stratification factor as covariates will be fitted. A point-estimate along with 2-sided 95% CI for HR of the intervention effect (in terms of relative risk reduction (RRR) = $100 \times [1 - \text{HR}] \%$) will be provided. The cumulative event rate derived from Kaplan-Meier estimate will also be displayed graphically to evaluate the timing of event occurrence and the consistency of the treatment effect over time.

REFERENCES

1. Berglund P and Heeringa S. Multiple Imputation of Missing Data Using SAS®. 2014. Cary, NC: SAS Institute Inc. CDISC. “Analysis Data.
4. International Council For Harmonisation (ICH) of Technical Requirement for Pharmaceuticals for Human Use (final version, 2019): ICH Harmonised Guideline – Addendum on estimands and sensitivity analysis in clinical trials (to the guideline on Statistical Principles for Clinical Trials) - E9 (R1).

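### The SAP starts the HRU window at informed consent and leaves the start of by-arm claims counts unresolved, so pre-dose events can enter and pull ratios toward 1

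*SAP*

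**What the plan says.** **HRU.** SAP 6.1 gives an analysis window, not only a collection window: "For the HRU data analysis, information collected from date of informed consent until the end of study will be considered in the final analysis". SAP 1.6 has the same start for collection: "The collection timeframe for claims associated with Health Resource Utilization will begin on the ICF Date through the 9-month observation period". SAP 9 compares the arms by "analyzing differences in hospitalizations/readmissions and ED visits using the Fisher exact test", and time to first hospitalization by a stratified log-rank test and a Cox model. SAP 5.4.2 plans Cox models for hospitalization and death "both for the double-blind treatment period and the entire study duration". None of these states a time origin. SAP 5.4.2 also says that HRU is described "separately for the double-blind treatment period and the observational (no intervention) period", and neither of those periods contains the time from consent to first dose.

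**Claims adverse events.** SAP 6.1 takes into account service dates "starting from the time informed consent is signed until the end of double-blind treatment plus 30 days". The same section says that claims events "will be analyzed separately for the 12-week treatment period + 30 days after last dose and the 9-month entire study period respectively", and that "A treatment emergent AE is defined as an event that occurs after the first dose of study intervention". The by-arm summary counts participants with an SAE or AE of interest and does not restrict these to treatment-emergent events. Events between consent and first dose are to be listed as well, but no sentence removes them from the by-arm counts.

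**The concern.** Treatment cannot affect an event that occurs before the first dose. Randomization balances such events between the arms in expectation but does not remove them. If they are counted, both arms gain the same expected number of events, and any rate ratio or ratio of proportions moves toward 1. For hospitalization the shift is away from an apparent benefit. For adverse events of interest it is toward an apparent absence of harm.

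There is also a reproducibility problem. Two programmers could follow different sentences of the SAP and produce different by-arm HRU tables. With enrollment now expected at about 400 to 480 instead of 1,900 (SAP 1.4), these comparisons have little precision to spare.

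**Working it through.** The documents give no event rate, sample size or power for HRU or claims events, so there is no stated figure to reproduce.

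**Inputs**
- Pre-dose time, lower figure: 21 days (SAP Table 1 and SAP Appendix 3, screening within 21 days before Day 1).
- Pre-dose time, upper figure: 28 + 7 = 35 days (protocol 4.2 and 5: up to 28 days of screening before randomization, then a 7-day baseline period that begins at randomization). The notes column of the protocol's Schedule of Activities counts screening as Day -28 to 0, which would give 28 days.
- Time from first dose: 84 days on treatment, 84 + 30 = 114 days, and 252 days to end of study (protocol 1.3).
- Assumptions: constant background rate, and full use of the pre-dose window by every participant. The true rate ratio (RR) of 0.70 is illustrative. The protocol cites 0.67 for heart failure hospitalization in the CANVAS program.

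**Formulas**
- Pre-dose share = pre / (pre + post).
- Ratio as read = (RR × post + pre) / (post + pre).

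| Days from first dose | Pre-dose days | Pre-dose share | RR 0.70 reads as |
|---|---|---|---|
| 84 | 21 | 21/105 = 20.0% | 79.8/105 = 0.760 |
| 84 | 35 | 35/119 = 29.4% | 93.8/119 = 0.788 |
| 114 | 21 | 21/135 = 15.6% | 100.8/135 = 0.747 |
| 114 | 35 | 35/149 = 23.5% | 114.8/149 = 0.770 |
| 252 | 21 | 21/273 = 7.7% | 197.4/273 = 0.723 |
| 252 | 35 | 35/287 = 12.2% | 211.4/287 = 0.737 |

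The table takes 0.70 as the true ratio over the whole period from first dose.

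**Harm, same formula.** A true ratio of 2.0 over 114 days would read (228 + 21)/135 = 1.84 or (228 + 35)/149 = 1.77.

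**Nine months, effect limited to the 84 treated days.**
- From first dose: (0.70 × 84 + 168)/252 = 226.8/252 = 0.90.
- From consent: 247.8/273 = 0.908 (21 days) or 261.8/287 = 0.912 (35 days).

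The untreated months do nearly all of the diluting, and the consent start adds about 0.01.

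**Proportion with at least one hospitalization over 84 days.** This uses an assumed rate of 0.8 per person-year, RR 0.67, 222 per arm (about half of the 445 discussed in SAP 1.4), p = 1 - exp(-rate × time), and a normal approximation to the Fisher test.
- From first dose: 16.8% versus 11.6%, difference 5.2 points, power 0.35.
- With 21 pre-dose days: difference 5.0 points, power 0.28.
- With 35 pre-dose days: difference 4.8 points, power 0.24.
- At assumed rates of 0.4 and 1.2 with 35 pre-dose days, power falls from 0.20 to 0.15 and from 0.47 to 0.32.

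**The case against.** The strongest reply is that the SAP already organizes these analyses around treatment. SAP 2.1 numbers study days from first dose. SAP 2 analyzes exploratory endpoints over the 12-week period and the 9-month duration. SAP 5.4.2 describes HRU by double-blind and no-intervention period. SAP 6.1 defines the by-arm adverse event summaries by treatment-based periods, uses a first-dose definition of treatment emergence and lists pre-dose events separately. On this view the consent wording only says which claims are pulled.

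For adverse events much of this stands. A reader might infer that the by-arm claims summaries are definitely counted from consent. The documents do not establish that. They leave it unresolved, because service dates from consent are also taken into account and nothing excludes pre-dose events.

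For HRU the reply is weaker. The SAP 6.1 sentence speaks of the final analysis, and the separate-period wording in SAP 5.4.2 conflicts with it without overriding it.

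A reader might also infer that the Cox and Kaplan-Meier clocks start at consent. The SAP does not say so; their origin is simply missing.

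The objections on size also stand. The 21 and 35 days are upper limits applied to everyone. The protocol requires clinically stable heart failure and excludes recent acute decompensation, so the pre-dose rate of heart failure events may be lower than the later rate. The 252-day rows of the table hold only if the effect persists for 6 months off drug.

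**Conclusion.** The point holds as a defect in the stated HRU window and as an unresolved inconsistency for claims adverse events and time-to-event origins. Read as written, up to 21 to 35 days of pre-dose time enter. That is 15.6% to 23.5% of the treatment-plus-30-day window, and a true ratio of 0.70 over that window would read at most 0.75 to 0.77. This rests on a constant event rate and full use of the screening window. If the effect ends with treatment, the 9-month ratio is barely changed by the choice of start.

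It would go too far to say that the plan hides harm or benefit. Pre-dose events favor neither arm, and the expected difference in mean counts is unchanged. The adverse event summaries are descriptive, and the HRU analyses are exploratory without multiplicity control. The KCCQ-TSS and step-count inferences are not affected.

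**What to change.** State one time origin for the by-arm HRU, claims SAE/AE and time-to-event analyses:
- **Safety set and FAS:** Study Day 1 (first dose). Both sets require at least one dose, so an earlier origin adds time in which no analyzed participant can have died. A randomization origin would also keep the shipping gap of up to 7 days.
- **All-randomized analysis, if one is run:** randomization.
- **Consent to the day before first dose:** report only in the separate listing that SAP 6.1 already plans.

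Then align SAP 1.6, 5.4.2, 6.1 and 9, keeping consent as the start of collection if wanted but not of the by-arm analysis. Reconcile the SAP's 21-day screening window with the protocol's 28 days plus 7-day baseline period.

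The cost is SAP wording and a date filter, with no new data. Slightly fewer events will be counted.
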